Medications taken after the first dose of study medication and through the last study-related activity will be documented on the appropriate CRF as concomitant medication. Prior and concomitant medications to be documented include but are not limited to: vitamins, herbal remedies (e.g., St. John's wort, valerian), over the counter and prescription medications.

Subjects will be instructed not to take any concomitant medication without first consulting the investigator or study coordinator throughout the duration of the study.

Prohibited Concomitant Medications:

The following medications and therapies are prohibited throughout the study (from signing of informed consent form [ICF] through the last study-related activity):

- Use of hormonal medications such as hormone therapy, HRT or hormonal contraception or any treatment for menopausal symptoms (prescription, over the counter or herbal).
- Investigational research products that have not been approved for any indication in the country where the subject is enrolled.
- Strong or moderate CYP1A2 inhibitors are prohibited.

Duration of Treatment:

Subject will take study drug daily from day 1 (randomization) for a duration of 52 weeks.

Formal Stopping Rules

Subject Discontinuation:

A subject **must** be withdrawn from the study treatment for any of the following reasons:

- Withdrawal of informed consent.
- Lost to follow-up.
- If for safety reasons it is in the best interest of the subject that she be withdrawn, in the investigator's opinion.
- Development of a medical condition that requires concomitant treatment with a prohibited therapy.
- Development of seizures or other convulsive disorders.
- Breaking of the randomization code during administration of the study drug by the investigator or by a member of the site staff. If the code is broken by the sponsor for safety reporting purposes or early time point analysis, the subject may remain in the study.
- Confirmed (within 72 hours from the notification of test result) decrease in platelets below 75,000 mm³, which does not normalize after 7 days or immediate withdrawal in case of platelets below 50,000 mm³.
- Development of severe hepatic abnormality defines as ALT or AST > 8 × ULN.
- Confirmed (within 72 hours from the notification of test result) severe hepatic abnormality defined as any of the following:
 - ALT or AST > 5 × ULN for more than 2 weeks;
 - ALT or AST > 3 × ULN **AND** TBL > 2 × ULN or INR > 1.5; or

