- p. For practical reasons, the timing of DXA may vary from the actual time of the visit, depending on the DXA availability (DXA appointment). The screening visit (days -35 to -1 [visit 1]) DXA can be performed once the subject has been deemed eligible based on screening laboratory tests, or at visit 2 but must be performed before randomization. The week 52 (visit 15) DXA should be performed between week 50 and week 52, inclusive. For subjects who are withdrawn from the study prior to completion, a DXA will be completed as soon as possible after study drug discontinuation (preferably within 2 weeks).
- q. For HBsAG, anti-HCV antibodies, anti-HBs antibodies, anti-HBc antibodies and anti-HIV antibodies.
- r. Pharmacodynamic samples will be taken predose (1 hour) at day 1 (visit 2), week 4 (visit 3), week 12 (visit 5), week 24 (visit 8), at week 52 (visit 15) and week 55 (visit 16). Markers include LH, FSH, E2, SHBG, androstenedione, dehydroepiandrosterone, estrone and testosterone.
- s. Pharmacokinetic samples to be taken predose at week 4 (visit 3), week 12 (visit 5), week 24 (visit 8), and at EOT/ED week 52 (visit 15) and at 1 to 3 hour postdose at week 4 (visit 3). A predose sample will be collected for any subject with a signal of elevated ($> 3 \times$ ULN) transaminases. For the week 52 (visit 15) PK/PD samples, the last dose of study drug should be administered the day prior to the week 52 (visit 15) visit. Sites should collect week 52 (visit 15) PK/PD samples approximately at the same time when study drug would typically be given on site.
- t. A clinician will administer the C-SSRS measure electronically at the clinic visit, prior to any invasive procedures. This will be administered electronically via the site tablet at screening, (visit 1), week 0 (visit 2), week 12 (visit 5), week 24 (visit 8), EOT/ED week 52 (visit 15) and the follow-up visit (week 55 [visit 16]).

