- u. ePRO assessments are self-administered electronically via the site tablet at the study site at week 0 (visit 2), week 4 (visit 3), week 12 (visit 5), week 24 (visit 8) and week 52 (visit 15). The ePRO assessments are administered before any other study assessments/procedures are performed; assessments at visit 2 must occur prior to randomization/first dosing; assessments at week 4 (visit 3), week 12 (visit 5), week 24 (visit 8) must occur prior to dosing; in the event a subject withdraws from the study, efforts to collect information on the site-based subject-reported outcome measures should be made before or shortly after discontinuation.
- v. Subjects will be assigned study drug as a kit containing either fezolinetant or placebo. Study drug intake will be done with a glass of room temperature tap water. The first intake of study drug will take place at the study site on day 1 (visit 2) under the supervision of the study staff. On study visit days (except for EOT/ED week 52 [visit 15]), the daily dose of study drug will be taken at the study site, under the supervision of the study staff, after collection of predose blood samples. On all other days throughout the treatment period, subjects will be instructed to take their study drug at home, in the morning with water.
- w. Subjects will be asked to return all unused study drug. Compliance of study drug intake will be assessed by counting returned study drug and recorded in the source documents and the IRT.
- x. AEs and intake of concomitant medication(s) will be monitored continuously from informed consent until the last study-related activity.
- y. Screening (visit 1), Randomization, week 0 (visit 2) and EOT/ED week 52 (visit 15) visits, must be conducted in the clinic and not home healthcare, telemedicine conferences or a local laboratory.

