5 TREATMENTS AND EVALUATION

5.1 Dosing and Administration of Study Drug(s) and Other Medication(s)

5.1.1 Dose/Dose Regimen and Administration Period

Subjects will be screening up to 35 days prior to randomization. Informed consent will be obtained prior to randomization and before any study-related procedures are performed.

Subjects will be assigned study drug as a kit containing either fezolinetant or placebo at visits indicated in the schedule of assessments. Study drug intake will be done with a glass of room temperature tap water in the morning. The first intake of study drug will take place at the study site on day 1 (visit 2) under the supervision of the study staff.

On study visit days (except for EOT/ED week 52 [visit 15]) study drug will be taken at the study site, under the supervision of the study staff, after collection of predose blood samples. On all other days throughout the treatment period, subjects will be instructed to take their dose of study drug at home with water, in the morning.

In the event of a missed dose, the subject should skip the missed dose and continue with the next scheduled dose.

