6.5 Analysis of Safety

Overall long-term safety of fezolinetant and the effect of fezolinetant on endometrial health will be the primary objective of this study. The safety assessments include adverse events, laboratory assessments, vital signs, C-SSRS, ECG, endometrial health assessment and imaging (mammogram, DXA, TVU). In all analysis of safety, the treatment group includes placebo, fezolinetant 30mg, fezolinetant 45mg and fezolinetant total will be presented by treatment group for SAF, unless specified otherwise. For analyses by visit, the analysis windows from Section 6.10.1 will be applied. Except for adverse events and follow-up visit data, only data up to one day after the last dose date will be considered for the analyses.

The baseline value for safety endpoint will be the last non-missing value taken on or prior to first dose of study drug unless otherwise noted.

Primary Safety Variables

- Frequency and severity of AEs.
- Percentage of subjects with endometrial hyperplasia.
- Percentage of subjects with endometrial cancer.

Secondary Safety Variables

- Change from baseline in endometrial thickness at 12 months.
- Percentage of subjects with disordered proliferative endometrium.
- Change from baseline in bone mass density (BMD) and trabecular bone score (TBS) at hip and spine at 12 months.
- Change from baseline to each timepoint in vital signs: sitting systolic and diastolic blood pressure and pulse rate.

- Change from baseline to each timepoint in laboratory tests: hematology, biochemistry and urinalysis.
- C-SSRS at each timepoint.
- Change from baseline to each timepoint in ECG parameters

Exploratory Safety Variables

- Change from baseline to specified time points in serum concentrations of sex hormones and sex hormone-binding globulin (SHBG) (week 4, 12, 24, 52 and 55).
- Plasma concentration of fezolinetant and the fezolinetant metabolite ESN259564 at specified timepoints (week 4, 12, 24 and 52).

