6.10 Additional Conventions

6.10.1 Analysis Windows

Study Day for analysis windows will be calculated as date of visit/assessment – first dose date +1.

Study Day for the follow-up (FUD) phase will be calculated as date of visit/assessment – last dose date of study treatment (Date of EOT).

Except for adverse events, for the analysis window (weeks prior to the follow-up period), the last day is always 1 day after the last day of exposure to double-blind treatment.

The end of overall treatment is defined as the last day of treatment +1 and the follow-up period begins at last overall treatment + 2 days and onward (Follow-up Study Day 2).

The data summary by visits will be done following the analysis windows specified in the table below:

Analysis	Scheduled	Analysis Windows (day)				
Visits	Day in Protocol	a)	b)	c)	d)	e)
Baseline	Day 1	Last non-missin	ng value on or prio	or to day 1 (inclu	sive)	
Week 2	Day 15	2 to 22				
Week 4	Day 29	23 to 43	2 to 43	2 to 57		
Week 8	Day 57	44 to 71	44 to 71			
Week 12	Day 85	72 to 99	72 to 99	58 to 127	2 to 127	
Week 16	Day 113	100 to 127	100 to 127			
Week 20	Day 141	128 to 155	128 to 155			
Week 24	Day 169	156 to 183	156 to 183	128 to 267	128 to 267	
Week 28	Day 197	184 to 211	184 to 211			
Week 32	Day 225	212 to 239	212 to 239			
Week 36	Day 253	240 to 267	240 to 267			
Week 40	Day 281	268 to 295	268 to 295			
Week 44	Day 309	296 to 323	296 to 323			
Week 48	Day 337	324 to 351	324 to 351			
Week 52	Day 365	352 to 376	352 to 376	268 to 376	268 to 376	2 to 376
Follow-up	Day 386	Last treatment + 2 days and onwards				

a) Apply to Clinical laboratory and urinalysis

b) Apply to Vital signs

- c) Apply to Blood PD/PK sample, EQ-5D-5L, MENQoL
- d) Apply to C-SSRS
- e) Apply to 12-lead ECG

For TVU and DXA, the week 52 analysis window is day 2 to last treatment + 30 days. For endometrial biopsy, refer to Section 6.5.5 for analysis window.

As a general rule, if more than one observation exists within the analysis window, the observation closest to the scheduled visit day will be selected for that visit. If there are two observations that have the same distance from the scheduled day, the value that is after the scheduled day will be selected in the analysis. If more than one observation is made on the same day, an average value if continuous or the worst value if categorical will be included in the analysis.

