The Follow Up visit (Week 55) will include all data collected beyond 1 day after the last dose of the study drug. If there are more than one value, then the value that is closest to Day 386 from the last dose of study drug will be selected for the analysis. The same logic will be applied as in above for more than one value.

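### The SAP's cap at last dose + 1 day leaves no slack at Visit 15, so a missed final dose or a late in-window visit moves ECG, laboratory, vital-sign, C-SSRS, hormone and PRO values out of Week 52

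*SAP*

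**What the plan says.** The general rule for safety data in SAP 6.5 is "Except for adverse events and follow-up visit data, only data up to one day after the last dose date will be considered for the analyses". SAP 6.10.1 carries the same limit into all windows before Follow-up: "the last day is always 1 day after the last day of exposure to double-blind treatment". SAP 6.4.3 applies those windows to MENQOL and EQ-5D-5L, so the limit reaches the PROs too. On the other side of the line, "The Follow Up visit (Week 55) will include all data collected beyond 1 day after the last dose of the study drug".

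The protocol fixes where Visit 15 falls. Section 5.1.1 says "On study visit days (except for EOT/ED week 52 [visit 15]) study drug will be taken at the study site". Footnote s of Table 1 says, for the PK/PD samples, that "the last dose of study drug should be administered the day prior to the week 52 (visit 15) visit". Table 1 schedules Visit 15 on Day 365 with a window of -14/+6 days, and the synopsis says "Subject will take study drug daily from day 1 (randomization) for a duration of 52 weeks".

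Some assessments have their own rule in the SAP: TEAEs to 21 days after last dose (6.5.1), endometrial biopsy within 30 days of last dose (6.5.5), TVU and DXA to last treatment + 30 days (6.10.1).

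**The concern.** An on-treatment cut-off should tolerate ordinary variation in the final visit. This one falls on the day where the protocol puts that visit, so a one-day departure changes the label of attended, in-window data.

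The effect differs by assessment:

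- **ECG.** Table 1 schedules it only at screening and at Visit 15/EOT/ED. A relabelled ECG is the subject's only scheduled post-baseline recording, and SAP 6.5.4 tabulates ECGs at treatment visits.
- **MENQOL and EQ-5D-5L.** They are not collected at Week 55, so the value drops out of the Week 52 analysis. For subjects who withdraw, footnote u says that efforts to collect PROs "should be made before or shortly after discontinuation"; the later of these fall outside the cap.
- **Laboratory, vital signs, C-SSRS and hormones.** They are repeated at Week 55, and that value replaces Visit 15 under the Follow-up selection rule if the visit is attended. If not, the Visit 15 value is itself reported as Follow-up.
- **Early discontinuation.** The SAP's ECG window opens at Day 2, which would admit early-discontinuation ECGs. The cap removes any taken 2 or more days after last dose.

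**Working it through.** **Inputs.** Follow-up day = visit date - last dose date (SAP 6.10.1); on treatment if 1 or less, Follow-up if 2 or more. Visit 15 may fall on Days 365 - 14 = 351 to 365 + 6 = 371. SAP Week 52 windows are Days 352-376 (laboratory, vital signs), 268-376 (PD/PK, PROs, C-SSRS) and 2-376 (ECG).

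**The plan as intended.** Visit 15 on Day 365, last dose Day 364: 365 - 364 = 1, so Week 52 for every assessment. This works, with no day to spare.

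**One missed final dose.** Last dose Day 363: 365 - 363 = 2, so Follow-up for laboratory, vital signs, C-SSRS, hormones, PROs and ECG. With Visit 15 on Days 351, 358, 368 or 371 and one missed final dose, the follow-up day is again 2. Biopsy, TVU and DXA stay in, since 2 is within 30 days.

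**No missed dose, late visit.** If dosing ends at 52 weeks, the last dose is on Day 52 x 7 = 364. Visit 15 on Day 366 gives 366 - 364 = 2, and on Day 371 gives 371 - 364 = 7. All six days from 366 to 371 are inside the protocol window and inside the SAP's window to Day 376, yet all become Follow-up. The 52-week duration and the rule of dosing until the day before the visit agree only for a visit on Day 365. If dosing continues to the day before a late visit, only a missed dose causes the shift. The protocol does not settle this, and the two passages need reconciling.

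**Fate within Follow-up.** SAP 6.10.1 selects the value nearest Day 386 from last dose, which mixes a study day with a last-dose origin. Take Visit 15 on Day 365, last dose Day 363, and Visit 16 at 3 weeks ± 3 days after last dose (+ 18, + 21 or + 24, so Day 381, 384 or 387):

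- Target study day 386: Visit 15 is 21 days away; Visit 16 is 5, 2 or 1.
- Target 386 days after last dose: Visit 15 is 384 away; Visit 16 is 368, 365 or 362.
- Target 21 days after last dose: Visit 15 is 19 away; Visit 16 is 3, 0 or 3.

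Visit 16 is selected under every reading.

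**Size, for illustration only.** The documents give neither a rate of missed final doses nor an expected completion rate. Assuming 80% complete, 0.80 x 580 = 464 per arm. If 1%, 5% or 10% of them miss the last dose: 0.01 x 464 = 4.6, 0.05 x 464 = 23.2, 0.10 x 464 = 46.4, or about 5, 23 and 46 per arm.

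**Room for a wider cap.** The latest in-window Visit 15 after 52 weeks of dosing is last dose + 7. Visit 16 is at + 18 or later on the timing above, so a cap at + 7 cannot take in Visit 16.

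**The case against.** The strongest reply is that last dose + 1 is a coherent on-treatment rule, used consistently in SAP 6.5, 6.5.2.1 and 6.10.1, and that it matches the scheduled visit. The protocol gives a half-life of 4-6 hours, so 2 days off drug is 48/6 = 8 to 48/4 = 12 half-lives and 7 days is 28 to 42. MENQOL recalls the last week, so at + 7 almost the whole recall period is off drug. This stands for MENQOL and hormones, and it argues against simply widening their main analysis. It is weaker for the safety summaries: an on-schedule Visit 15, about 24 hours after dosing, is already 4 to 6 half-lives out, so the cap does not cleanly separate on-drug from off-drug values.

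It can also be said that laboratory tests and vital signs are taken about every 4 weeks, that these data are listed, that clinically significant changes are reported as AEs, and that MMRM uses earlier visits when Week 52 is missing. All true, and it limits the harm. It does not help ECG, which has no other scheduled post-baseline recording.

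The footnote on last-dose timing is a recommendation tied to PK/PD samples; a home dose on the visit day would give one day of slack. SAP 6.10.1 also glosses the last dose date as the date of EOT; if that meant the visit date, no shift would occur. But 6.5 and 6.10.1 also state the cap from the last dose date and the last day of exposure, so the gloss needs defining and does not remove the problem.

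A reader might infer that the entire Week 52 visit is lost, primary endpoints included. The separate windows for AEs, biopsy, TVU and DXA rule that out.

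**Conclusion.** The point holds for ECG, laboratory tests, vital signs, C-SSRS, hormones and PROs at Visit 15/EOT/ED. It matters most for ECG. It does not touch the primary endpoints, the endometrial endpoints or the bone endpoints, and PK concentrations are only listed under the SAP.

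Three further inferences are not supported. Week 52 is not singled out for ECG, laboratory, vital signs or C-SSRS: SAP 5.2 attaches 12 months only to endometrial thickness and BMD/TBS. A difference in loss between arms is possible but not shown. The figure of about 5 to 46 per arm rests wholly on the assumed 1% to 10% and 80%, and is not an estimate. No count can be given for early discontinuers, because the documents do not say how long after last dose their visits occur.

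This is a worthwhile correction of moderate weight, best made before database lock.

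**What to change.** 1. In SAP 6.5 and 6.10.1, for ECG, laboratory, vital-sign and C-SSRS values collected at Visit 15/EOT/ED, extend the cap to last dose + 7 days and start Follow-up the day after. Flag values taken more than 1 day after last dose and give a sensitivity summary without them.
2. For MENQOL, EQ-5D-5L and hormones, keep the + 1 day main analysis and add a supplementary Week 52 analysis that includes Visit 15/ED values up to + 7 days.
3. Leave the period of the liver peak table in 6.5.2.1 unchanged, and say so, because a transaminase value at + 2 to + 7 would then appear in the Week 52 laboratory summary but not in that table.
4. Name the biopsy, TVU and DXA windows as exceptions in the SAP 6.5 sentence, which read literally exempts only AEs and follow-up data. Define last dose date (date of EOT) as the date of the last dose taken.

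The cost is SAP wording, a flag, and a few extra summaries. A few values taken 2 to 7 days off drug enter the Week 52 safety summaries, visibly. Early-discontinuation visits later than + 7 days remain outside.

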7.6 Analysis of Safety

Overall long-term safety of fezolinetant will be the primary objective of this study. The safety assessments include adverse events, laboratory assessments, vital signs, C-SSRS, Pap test, physical examination, ECG, endometrial health assessment and imaging (mammogram, DXA, TVU). Safety analysis will be conducted on the SAF.

Primary Safety Variables:

The primary variable will require the evaluation of the safety of fezolinetant on the following:

- Frequency and severity of AEs
- Percentage of subjects with endometrial hyperplasia
- Percentage of subjects with endometrial cancer

Secondary Safety Variables:

- Change from baseline in endometrial thickness at 12 months
- Percentage of subjects with disordered proliferative endometrium
- Change from baseline in BMD and TBS at hip and spine at 12 months
- Vital signs: sitting systolic and diastolic blood pressure and pulse rate
- Laboratory tests: hematology, biochemistry and urinalysis
- C-SSRS
- ECG parameters

For each AE of special interests a summary statistics will be provided and the rate, odds ratio, and their corresponding 2-sided 95% confidence intervals will be presented. For the treatment comparison of bone density and endometrial thickness, an analysis of covariance model will be used. The model will include treatment and smoking status (current vs former/never) as factors, with baseline weight and baseline as covariates.

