This change is made to further optimize the collection of EOT/ED endometrial biopsies for the primary objective/endpoint of the study and provide clarity on when a repeat biopsy is required.
3. Add Clarification for Pharmacokinetic Sample at Week 52
DESCRIPTION OF CHANGE:
A statement added to the footnote for Blood Pharmacokinetic Sample in the schedule of assessments to clarify that the last dose of study drug should be administered the day prior to the week 52 (visit 15) visit.
RATIONALE:
This revision is made for clarification.
4. Update Timing of Week 52 Dual-Energy X-Ray Absorptiometry (DXA)
DESCRIPTION OF CHANGE:
In Section 5.5.2 and the schedule of assessments, the timing of the week 52 DXA is changed to ‘between week 50 and 52.’

RATIONALE:
This revision is made to align with the timing of the adjusted Visit 15/EOT/ED visit window.
5. Clarification of Recording an Abnormal Endometrial Biopsy as an Adverse Event (AE)
DESCRIPTION OF CHANGE:
Added that the investigator should record any abnormal biopsies and the associated diagnostic and therapeutic measures, as an AE.
RATIONALE:
Clarification provided to investigator so abnormal endometrial biopsies can be followed to resolution.
6. Removed Platelet Reduction as AE of Special Interest
DESCRIPTION OF CHANGE:
Platelet reduction is removed as an AE of special interest
RATIONALE:
Not consistent with the statistical analysis plan.
7. Removed Significance Testing
DESCRIPTION OF CHANGE:
Removed the significance testing for dichotomized endpoints.
RATIONALE:
The confidence intervals for odds ratio and rate is sufficient for interpretation.
8. Add Appendix for Clinical Study Continuity
DESCRIPTION OF CHANGE:
A Clinical Study Continuity appendix is added to the protocol (Appendix 12.7). This appendix contains procedures for continuity of care during a crisis (e.g., natural disaster or a pandemic).
RATIONALE:
This appendix is added to provide acceptable alternate methods to assess safety and efficacy parameters in the event the clinical study is interrupted at the country, state, site or participant level during any crisis (e.g., natural disaster or pandemic). This is an appendix that is being standardized throughout Astellas. The procedures that are included in this appendix are aligned with what was already included in the previous version of the protocol.

9. Minor Administrative-type Changes
DESCRIPTION OF CHANGE:

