In general, summary statistics will be provided for all the safety parameters. Treatment comparisons will be performed for endometrial and bone density related endpoints. For AESI, the rate, odds ratio and their corresponding 95% exact confidence intervals will be presented, which will be constructed based on Santner-Snell approach. An ANCOVA model, with treatment and strata smoking status (current vs former/never) as factors, with baseline weight and baseline as covariates, will be used for single assessment continuous endpoints. Each following section will specify the analysis method appropriately.

The change and percentage reduction in serum concentrations of sex hormones and sex hormone-binding globulin (SHBG) from baseline to each analysis visit will be summarized.

For hormone related parameters, if the value is below the low limit of quantification, the value will be imputed as half of the LLOQ. In addition, the percentage of subjects who have BLOQ values at baseline who then have measurable post-baseline values will be summarized.

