6.5.1 Adverse Events

Per protocol, a treatment emergent adverse event (TEAE) is defined as the AEs that occurred on or after first dose of study drug and 21 days after the last dose of study drug (when AE collection closes).

A study drug-related TEAE is defined as any TEAE with a causal relationship of YES by the investigator.

The sponsor has a list of events that they classify as "always serious" events. If an AE is reported that is considered by the sponsor to be an SAE per this classification as "always serious", the AE will be treated as an SAE in tables and listings, and flagged as 'always serious' in AE listings.

An overview table will include the following

- Number of TEAEs,
- Number and percentage of subjects with TEAEs,
- Number of drug related TEAEs,
- Number and percentage of subjects with causally drug related TEAEs,
- Number of serious TEAEs,

- Number and percentage of subjects with serious TEAEs,
- Number of serious drug related TEAEs,
- Number and percentage of subjects with serious drug related TEAEs,
- Number of TEAEs leading to permanent discontinuation of study drug,
- Number and percentage of subjects with TEAEs leading to permanent discontinuation of study drug, and
- Number of deaths.

In order to adjust for differences in subjects' durations and the potential differential dropout rates between the treatment groups, an overview table to report exposure adjusted incidence rate (per 100 subject-years) for the above AE categories will be summarized. The total subject-years of exposure is calculated as the sum over subjects of the total duration of exposure divided by 365.25:

$$\sum_{i} \frac{ld_i - fd_i + 1}{365.25},$$

where fd_i and ld_i denote the first dose date of study drug and the last dose date of study drug for subject *i*.

The number and percentage of subjects with TEAEs in the following AE categories will be summarized for each treatment group by system organ class (SOC), high level term (HLT) and preferred term (PT):

- TEAEs
- drug related TEAEs.

The number and percentage of subjects with TEAEs in the following AE categories will be summarized by SOC and PT:

- serious TEAEs,
- drug related serious TEAEs,
- TEAEs leading to permanent discontinuation of study drug,
- drug related TEAEs leading to permanent discontinuation of study drug,
- TEAEs that equal to or exceed a threshold of 5.0% in any treatment group (threshold is based on PT).

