- TEAEs excluding serious adverse events that equal to or exceed a threshold of 5.0% in any treatment group.

The number and percentage of subjects with TEAEs, as classified by PT only, will be summarized for each treatment group.

The number of TEAEs and the number and percentage of subjects with TEAEs, as classified by SOC and PT will be summarized by severity and by relationship to study drug. In the subject count, if a subject has multiple TEAEs with the same SOC or PT, but with differing severity or relationship, then the subject will be counted once with the worst severity and highest degree of relationship. If severity or relationship is missing for all episodes of the event, the subject will be counted under missing severity or relationship. In the adverse event count, the adverse events will be presented in each category they were classified to. Drug related TEAEs will be presented in a similar way by severity only.

Among TEAEs, following adverse events of special interest (AESI) are defined:

- Adverse event of endometrial hyperplasia/cancer or disordered proliferative endometrium
- Adverse event of liver test elevations
- Adverse event of uterine bleeding
- Adverse event of thrombocytopenia
- Adverse event of bone fractures
- Adverse event of abuse liability
- Adverse event of depression
- Adverse event of wakefulness
- Adverse event of effect on memory

Search terms defining the AESIs will be pre-specified and documented. The number and percentage of subjects with AESIs as classified by PT will be separately summarized for each treatment group.

The number and percentage of subjects with TEAEs associated with COVID-19, as classified by PT, will be summarized for each treatment group, fezolinetant total and overall.

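### The exposure-adjusted incidence planned in SAP 6.5.1 leaves out the AESIs, the only adverse events given a between-arm estimate (minor)

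*SAP*

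**What the plan says.** SAP 6.5.1 gives its reason for exposure adjustment as differing durations and "the potential differential dropout rates between the treatment groups". It then limits the adjustment: "an overview table to report exposure adjusted incidence rate (per 100 subject-years) for the above AE categories will be summarized". Those categories are TEAEs, drug-related TEAEs, serious TEAEs, serious drug-related TEAEs, TEAEs leading to permanent discontinuation, and deaths. The denominator is total subject-years, built from dates that "denote the first dose date of study drug and the last dose date of study drug".

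The nine AESIs are defined later in the same section and have no row in that table. For them, "The number and percentage of subjects with AESIs as classified by PT will be separately summarized for each treatment group". SAP 6.5 adds the between-arm estimate: "For AESI, the rate, odds ratio and their corresponding 95% exact confidence intervals will be presented". Protocol 7.6 agrees: "the rate, odds ratio, and their corresponding 2-sided 95% confidence intervals will be presented". Neither document describes a person-time or time-to-event analysis of AESIs.

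The word rate is not defined for AESIs. SAP 6.5.1 specifies number and percentage, and Protocol 7.6.6 equates rates with percentages of subjects for the biopsy outcomes, so I read it as a proportion.

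**The concern.** The SAP names a problem, unequal exposure, and handles it for broad AE totals that carry no between-arm estimate. It does not handle it for the AEs it chose to compare. Protocol Attachment 1, item 7, dropped significance tests for dichotomised endpoints on the ground that "The confidence intervals for odds ratio and rate is sufficient for interpretation", so for AESIs these are the figures a reader will use.

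TEAEs are "the AEs that occurred on or after first dose of study drug and 21 days after the last dose of study drug". A woman who stops early therefore has less time in which uterine bleeding, a fracture or depression can be recorded. If one arm drops out more, its AESI percentage falls a little for that reason alone, and that arm looks slightly safer. The odds ratio takes no account of this.

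**Working it through.** **The plan's own figure first.** Protocol 7.1 and SAP 3 tabulate the chance of seeing events among 580 women per arm. At 0.9%, the chance of at least one is 1 − 0.991^580 = 99.47%, as printed. All 27 cells reproduce, with a largest difference of 0.004 percentage points. The plan gives no figure for exposure-adjusted AESI rates.

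**Inputs.**
- From the documents: n = 580 per arm; 52 weeks of treatment, taken as 1 year; AE collection to 21 days after last dose (21/365.25 = 0.0575 years).
- Assumed: 52-week completion c by arm; exponential dropout; constant AESI hazard λ; no true effect. The rates 0.5% and 0.9% per year lie within the plan's table; 3% is an assumed upper value.
- The only arm-specific completion figures in the documents come from the 12-week phase 2b study (Protocol 2.2.2): 84% on placebo and 80% on fezolinetant.

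**Formulas.**
- Dropout hazard H = −ln(c); mean exposure E = (1 − c)/H. This gives E = 0.896 years at 80%, 0.869 at 75% and 0.841 at 70%.
- Crude risk p = ∫₀¹ H·exp(−Hx)·[1 − exp(−λ(x + 0.0575))] dx + c·[1 − exp(−1.0575λ)].
- Odds ratio from p in each arm, with a Wald 95% CI. Existing SAP rate = p/E.

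**Results, placebo vs fezolinetant** (shifts taken before rounding):

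| λ per year | Completion | Expected events | Shift | Odds ratio (95% CI) | Rate ratio, SAP denominator |
|---|---|---|---|---|---|
| 0.5% | 80% vs 75% | 2.76 vs 2.68 | 0.08 | 0.97 (0.18–5.24) | 1.002 |
| 0.9% | 80% vs 75% | 4.96 vs 4.81 | 0.14 | 0.97 (0.28–3.42) | 1.002 |
| 0.9% | 80% vs 70% | 4.96 vs 4.67 | 0.29 | 0.94 (0.26–3.35) | 1.004 |
| 3% | 80% vs 75% | 16.35 vs 15.88 | 0.46 | 0.97 (0.48–1.96) | 1.002 |
| 3% | 80% vs 70% | 16.35 vs 15.41 | 0.94 | 0.94 (0.46–1.91) | 1.004 |

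A hand check for rare events: the odds ratio is close to the ratio of mean observation times, (0.869 + 0.0575)/(0.896 + 0.0575) = 0.97.

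Reversing the imbalance (70% placebo, 80% fezolinetant) gives 1.06. Applying the phase 2b completion figures to 52 weeks gives 0.98. With a true hazard ratio of 2 at 0.9% per year, the odds ratio is 1.95 (80% vs 75%) or 1.89 (80% vs 70%), against 2.01 with full follow-up.

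**Level of the adjusted rate.** The SAP denominator stops at last dose, while events count for 21 days more. At 80% completion the rate is therefore 0.953 rather than 0.90 per 100 subject-years (about 6% high), and 3.14 rather than 3.00 (about 5% high). The excess is nearly equal in each arm, so the ratio is barely touched.

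**Where constant hazard fails.** For rare events the SAP-denominator rate ratio is roughly the odds ratio times the inverse ratio of mean exposures: 0.896/0.869 = 1.031, or 0.896/0.841 = 1.065.
- Events only in weeks 4 to 8: odds ratio 0.996 or 0.992, but rate ratio about 1.03 or 1.06. The crude result is better.
- Events only in months 7 to 12: odds ratio 0.96 or 0.91, rate ratio about 0.99 or 0.97. Adjustment removes most of the shift, not all of it.

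**The case against.** The strongest reply is that this changes nothing a reader would conclude. At 0.9% per year and 80% vs 75% completion, the shift is 0.14 event among 580 women, or 0.024 percentage points. The SAP plans exact intervals; as a stand-in, a conditional exact interval at 5 vs 5 events is about 0.23 to 4.37, wider than the Wald interval used above. This stands, and it fixes the severity.

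Second, an adjusted AESI rate can be roughly recovered from planned outputs by dividing AESI counts by subject-years, and the disposition and exposure summaries (SAP 6.2.1, 6.3) would show any imbalance. This also stands: what is missing is a prespecified display, not the data.

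Third, a percentage over the on-treatment period plus 21 days validly describes what was observed. It is off only against a target of equal follow-up, which the plan does not set for AESIs. That is fair, but the SAP adopts the same target for the overview categories.

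Fourth, exposure adjustment does not suit every AESI. SAP 6.5.5 largely handles the biopsy outcomes by requiring a satisfactory result on or after Day 326 or an earlier abnormal diagnosis. The main phase 2b transaminase pattern fell between weeks 4 and 8 (Protocol 1.5), and liver and platelet thresholds force withdrawal (Protocol 6.1), so the event itself shortens exposure. This stands and shapes the footnote below.

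A reader might infer that the AESI odds ratios will make fezolinetant look safer than it is. The documents do not support that. They give no dropout by arm for this trial, the direction could be either way, and no test rests on the odds ratio.

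**Conclusion.** The inconsistency is in the text: exposure adjustment is planned for a stated reason and then not carried to the AEs that are compared between arms. Its effect is small and conditional. With no true effect, a constant hazard and exponential dropout, the odds ratio is about 0.97 at 80% vs 75% completion and 0.94 at 80% vs 70%. Across the rates examined that is 0.08 to 0.94 of an event per arm. The completion figures and the 3% rate are assumptions. The point concerns AESIs that accrue over the year, not early liver elevations or the biopsy outcomes. It is an optional improvement at the lowest severity.

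**What to change.** In SAP 6.5.1, add one row per AESI to the planned exposure-adjusted incidence table: subjects with at least one event divided by the subject-years already defined there, per 100 subject-years, by arm. Keep the planned percentage and odds ratio. No second at-risk denominator and no added set of score intervals is needed, since the existing denominator already gives null rate ratios of 1.002 to 1.004 in the constant-hazard scenarios above.

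Footnote the rows as follows:
- The rates assume a roughly constant hazard and non-informative dropout.
- Biopsy outcomes are read from the endometrial health set.
- Early or withdrawal-triggering events (liver elevations, thrombocytopenia) are read from the crude percentage and odds ratio.

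The cost is SAP wording and nine rows from data already collected, some on sparse counts. The rates will run about 5% to 6% high in every arm because the denominator omits the 21-day window; the footnote should say so.
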